Procedures. Participants will first be asked questions about their mental health needs, challenges they face accessing care, and strategies they have used to manage their mental health. All participants will then be shown App Store descriptions of ten apps that have received the highest rating by PsyberGuide, a non-profit company that consistently rates existing apps for their safety, data privacy and user ratings. Participants will provide initial impressions on the acceptability and feasibility of using these apps. We will then ask participants if they would be willing to participate in a randomized trial to test these apps, with the aim of recruiting 1000 participants. Participants will be randomized (100 per group) to one of the ten apps. They will be asked to download their assigned app and use it for 4 weeks. We selected four weeks because (1) this is ample time to determine the usability, acceptability and feasibility of these apps (2) based on past remote research, this is when we will see the first effects of apps on mental health outcomes and (3) also based on past research, this is the longest period of time we will be able to maintain a 100-80% of the

sample. After 4 weeks of use, participants will be asked to provide an evaluation of acceptability, feasibility and usability of the app, how often they used the app, and if they found the app helpful. They will also complete PHQ9, GAD7, and brief Difficulties with Emotion Regulation Scale (DERS) and four measures from the IMV model of suicidal behavior – defeat, entrapment, thwarted belongingness, and perceived burdensomeness. The Suicidal Behaviors Questionnaire-Revised (SBQ-R), a four-item self-report that assesses suicide attempts, ideation, communication, and intent since the last assessment. Given some limitations of the attempt item in the SBQ-R (which is combined with suicidal ideation), an additional item "Have you attempted to kill yourself?" will be added. This single-item has been demonstrated to identify a research rated suicide attempt in 89.3% of cases. We will also ask if they used any other mental health apps or services during this 4-week period.

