T-tests and chi-square tests will compare demographic and baseline clinical outcomes by missing data status at follow-up timepoint. Chi-square tests will examine the association between condition assignment and compliance (whether a participant used the app they were assigned to or used an alternative app). All analyses are intent-to-treat. Sensitivity analyses will be conducted excluding those who never downloaded or used the app they were assigned. Analyses of variance will be used to compare conditions on AIM, IAM, and IUS scores at follow-up. A series of mixed effects models using restricted maximum likelihood estimation will be built to test linear time change on the PHQ-9, GAD-7, and DERS-SF, and to test for condition differences at follow-up and change slope. Models will be built in an outwardly nested fashion, such that an initial null model was computed, followed by models that add a random intercept, random time component, condition assignment, and condition x time interaction effects. To test whether there was a dose-response relationship such that the app use frequency was associated with rate of change on PHQ-9, GAD-7, and DERS-SF scores, we will compute another series of mixed effects models for each outcome. An initial model will include variables for time and frequency of use, a second model will add condition terms for each app using Beautiful Mind as reference, a third model will add condition x frequency interaction terms for each app, and the fourth model will include time, frequency, and a time x frequency interaction term. Model comparisons will apply -2 Log Likelihood, Akaike Information Criterion, and Bayesian Information deviance statistics. To test the impact of app use frequency on change over time, similar nested model testing will be applied using an initial null model, followed by models that added dosage, dosage x time interaction, and condition assignment.

Sample Size and Power. A priori power analysis for an ANOVA *F* test indicated that a sample size of 1,000 (n=200 participants in each of the active and control app conditions) would be sufficient with a power of .80 and an alpha of .05 for a minimum detectable effect size (MDES) of Cohen's d=.24 for main effect comparisons between any two conditions.

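### The users-only sensitivity analysis excludes people on a post-randomisation event, so if uptake differs by app its app comparisons can reflect selection and should not be used to rank apps.

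*Combined protocol and SAP*

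**What the plan says.** The Analysis section of the combined protocol and SAP sets the main population: "All analyses are intent-to-treat". The next sentence gives the only analysis that the plan calls a sensitivity analysis: "Sensitivity analyses will be conducted excluding those who never downloaded or used the app they were assigned". Just before these two, the plan provides for a check on uptake: "Chi-square tests will examine the association between condition assignment and compliance". It does not say what follows for the users-only analysis if that test shows a difference. No weighting, covariate adjustment or complier-average effect is specified for the reduced population, and nothing limits app-to-app comparison within it.

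The design is described under Procedures: "Participants will be randomized (100 per group) to one of the ten apps". Before randomisation, every participant sees the store descriptions of all ten apps and gives first impressions of their acceptability and feasibility. How often the assigned app was used is asked after four weeks. Question 3 under Aim 1 asks which apps improve depression, anxiety and emotion regulation, so the comparison of interest is app against app.

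**The concern.** Whether someone ever starts the assigned app is decided after allocation and may depend on the app. Each arm then has its own filter: the users of one app are the people willing to start that app, and the users of another are the people willing to start the other. If one app is started by half its arm and another by nearly all, the two user groups are different kinds of people and randomisation no longer protects the comparison.

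Two conditions are needed for bias: uptake must differ by app, and what drives uptake must also predict outcome. If both hold, the users-only result can disagree with intent-to-treat when no app is better than any other, and agreement is not clear reassurance either. The results are meant for rapid release to suicide-prevention organisations and public-health partners. A list of apps ordered by results among users could be read as a ranking of effectiveness.

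**Working it through.** **Is there a plan figure to reproduce?** The documents give no uptake rate, no expected difference in uptake and no motivation-outcome correlation. The only effect size is in Sample Size and Power: "minimum detectable effect size (MDES) of Cohen's d=.24 for main effect comparisons between any two conditions". It is not a sound yardstick here. It is stated for 200 per condition, whereas Procedures gives 100. With two-sided alpha .05 and power .80, the detectable d is (1.960 + 0.842) × √(2/n). That is .28 at n = 200 and .40 at n = 100, and d = .24 would need 2 × (2.802/.24)² ≈ 273 per arm. The bias is therefore reported in SD units and as a false-positive rate.

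**Inputs from the documents.** Ten apps, 100 per group, exclusion of those who never start.

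**Inputs assumed.** All apps equally effective; uptake spread evenly from 50% to 90%; correlation r between motivation and improvement of .2 to .4; correlation ρ between motivation and propensity to start the app of .5 or 1; complete follow-up.

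**Model.** Motivation and propensity to start are standard normal with correlation ρ. In an arm with uptake p, the top share p on propensity become users. The expected improvement among users, in SD units relative to the whole arm, is

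shift(p) = r × ρ × φ(z)/p, where z is the (1 − p) normal quantile.

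- p = .50: φ(0)/.50 = .399/.50 = .798
- p = .90: φ(1.282)/.90 = .1755/.90 = .195
- Difference: .603, so the spurious gap is .603 × r × ρ.

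**Results for 50% to 90% uptake** (rejection rates from simulated trials with no true differences; intent-to-treat stays near 5% throughout):

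| r | Gap, ρ = 1 | Users-only omnibus rejection, ρ = 1 | Gap, ρ = .5 | Users-only omnibus rejection, ρ = .5 |
|---|---|---|---|---|
| .2 | .12 | 8% | .06 | about 6% |
| .3 | .18 | 14% | .09 | 6% to 7% |
| .4 | .24 | 24% | .12 | 8% to 9% |

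ρ = 1 means that motivation alone decides who starts, which is the extreme case.

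**Sensitivity to the uptake spread, at r = .3 and ρ = 1.**
- Uptake 70% to 90%: the factor is .497 − .195 = .302, the gap .302 × .3 = .09 SD, and rejection about 7%.
- One app at 30% and the other nine at 80%: the gap is .348 − .105 = .24 SD, and rejection 11%.

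**Ranking.** With 50% to 90% uptake and ρ = 1, the lowest-uptake app comes first among users in about 27% of trials at r = .3, against about 10% under intent-to-treat. Some of that excess is noise from a smaller group: at r = 0 the figure is already about 13%.

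**Direction.** A negative r keeps each gap's size and reverses its sign.

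**Does weighting help?** Weighting users by inverse probability of use, on predictors measured before randomisation, was tried at r = .3. It cut the gap from .18 to between .14 and .17 SD when motivation alone decides uptake, and from .09 to between .02 and .07 SD under the weaker selection.

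**The case against.** The strongest reply is that the plan already ranks the analyses correctly. Intent-to-treat governs, the users-only run is labelled as sensitivity, and uptake by condition will be tested. The documents do not say that the users-only run is meant to confirm a ranking, nor that readers will prefer it. This stands, and it confines the problem to a secondary analysis. It does not remove the problem, because the plan attaches no consequence to the uptake test and places no limit on comparing apps among users.

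The second reply is that the size is invented. That also stands: the uptake spread and correlations are assumptions. With moderate selection, or with uptake between 70% and 90%, the false-positive rate at r = .3 is only a little above 5%.

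Four stronger readings are tempting, and the documents do not support them.
- **That apps people abandon will look best.** The exclusion covers people who never start; those who try the app and stop are kept.
- **That the bias always favours low-uptake apps.** This needs keener users to improve more, and the documents give no evidence either way.
- **That the bias matches the trial's detectable effect.** The .24 figure is stated for 200 per condition and does not reproduce there, so the match at r = .4 is a coincidence.
- **That the lowest-uptake app will usually come first.** In the 50% to 90% setting it does so in a minority of trials.

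The third reply concerns the remedy. If motivation alone decided uptake, non-users would have no chance of being users, and weighting could not recover them. Motivation is not measured directly, and app ratings are at best a proxy. This is right, and it is why weighting cannot be the main safeguard.

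**Conclusion.** The concern holds in a limited form. The one named sensitivity analysis selects on a post-randomisation event that the plan itself expects may vary by app, and nothing restores comparability or restricts its use. If uptake differs and its drivers predict outcome, app comparisons among users are not randomised comparisons. At a motivation-outcome correlation of .3 with uptake from 50% to 90%, the spurious gap is about .09 SD under moderate selection and up to .18 SD under complete selection. The omnibus test then rejects in about 6% to 7% and 14% of trials. These sizes depend wholly on assumed inputs, and the direction depends on whether keener users do better or worse. A reader might infer that the trial's main conclusions are compromised; they are not, because those rest on intent-to-treat. This is a change worth making, not a fault that invalidates the plan.

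**What to change.** In order of importance:

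1. State in the Analysis section that app-to-app conclusions and any ranking come only from the intent-to-treat analysis.
2. Label the users-only analysis as a non-randomised comparison, and print each app's uptake beside its users-only result.
3. Replace the unadjusted users-only comparison with one weighted by inverse probability of use, or adjusted, on data that predate randomisation: baseline symptom scores, employment group (essential worker or unemployed), and the participant's first acceptability and feasibility ratings of the app later assigned. Specify the model in advance. Because use is asked at four weeks, also state how people with no follow-up report are classified.

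The first two cost a few sentences and one table column. The third costs one logistic model and slightly wider intervals, and needs no new data collection. It removes only the part of the bias that the measured predictors explain, so the weighted result must not be presented as unbiased.

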Question 1: Which mental health apps will be deemed to be acceptable (Acceptability of Intervention Measure), Feasible (Intervention Feasibility Measure), and Usable (Intervention Usability Measure) by essential workers and the unemployed?

Question 2: What features of these interventions did participants find particularly helpful?

Question 3: Which apps result in reduced depression (PHQ-9), anxiety (GAD-7) and better emotional regulation (DERS)?

Aim 2: To disseminate our findings and recommendations through national partnerships, the UWAC website, the ALACRITY Centers network, CSPAR and suicide prevention organizations, and WA state DPH.

Methods

Participants. Participants will be recruited in three ways: (1) mTurk; (2) MHA ads; and (3) Facebook Ads. We will aim to recruit 2,000 participants over the course of one week. Based on our past research, this sample is feasible to recruit in our proposed time frame. We have been able to recruit samples larger than this in 3 weeks using all of these methods. Participants will be eligible if (1) they are an essential worker or unemployed due to COVID19; (2) they have a past history of mental health issues or experiencing suicide ideation motivational risk factors based on the Integrated Motivational-Volitional (IMV) Model of Suicidal Behaviour. Participants will be compensated for their participation in this study.

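### The condition tests on PHQ-9, GAD-7 and DERS-SF ignore the common baseline that randomisation provides, and none is named as deciding; specify one common-baseline model per outcome with a joint week-4 test.

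*Combined protocol and SAP*

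**What the plan says.** Aim 1, Question 3 asks: "Which apps result in reduced depression (PHQ-9), anxiety (GAD-7) and better emotional regulation (DERS". Under Procedures, "Participants will be randomized (100 per group) to one of the ten apps", with one follow-up after 4 weeks. The three scales are listed at that follow-up: "They will also complete PHQ9, GAD7, and brief Difficulties with Emotion Regulation Scale (DERS". Procedures does not list them before randomisation, but the Analysis section presumes baseline values, because it will "compare demographic and baseline clinical outcomes by missing data status at follow-up timepoint".

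The Analysis section fits REML mixed models "to test for condition differences at follow-up and change slope". A null model is "followed by models that add a random intercept, random time component, condition assignment, and condition x time interaction effects". The two dose-response series also enter condition as a main effect. No baseline covariate, ANCOVA or constraint on baseline means appears anywhere. Models are to be compared by -2 log likelihood, AIC and BIC, and no single condition test per outcome is named as deciding.

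The power paragraph refers to 200 per condition, d=.24 and "main effect comparisons between any two conditions".

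**The concern.** With a baseline and one follow-up, a model with free condition and condition x time terms yields two contrasts. With complete data, the follow-up contrast ignores baseline altogether, and the change contrast subtracts it with weight 1. When the variances at the two waves are equal, the efficient weight is the correlation r. Randomisation makes the expected baseline means equal, and neither contrast uses this.

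The step that has condition but no interaction gives a third estimate. With complete data and equal variances, it is the average of the baseline and week-4 differences, so it shows half of an effect present only at week 4. The plan does not say that this term will be reported as the app effect, but it does not exclude it, and the power paragraph speaks of main effects.

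At stake are precision in a trial with small arms, and clarity about which number answers Question 3.

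A minor related point concerns the random time step. Two waves give three second moments (two variances and one covariance). A random intercept, a random slope, their covariance and a residual are four parameters. If the covariance is set to zero with 0/1 time coding, the slope variance is only the rise in variance from baseline to week 4, or 0 if variance falls. The fixed condition effects are not biased by this.

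**Working it through.** **Inputs.** From the documents: ten apps of 100 (Procedures) or 200 per condition with 1,000 in total, hence five conditions (Sample Size and Power); alpha .05; d=.24; retention of 80 to 100% at 4 weeks (Procedures). Assumed: two-sided tests, equal SDs at both waves, ignorable dropout, and r=.3/.5/.7.

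**The plan's own figure.** At 200 per condition, an unadjusted two-sided pairwise comparison has an MDES of .281 and 67% power at d=.24, so the stated .24 does not reproduce. A common-baseline contrast at r=.5 gives .243, and .24 exactly at r of about .52, but neither the adjustment nor r is in the plan.

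**Variance per arm**, in SD² units, with N randomised and n followed up:
- follow-up: (1-r²)/n + r²/N
- change: (1-r²)/n + (1-r)²/N
- common baseline: (1-r²)/n
- condition step without interaction: let S00=1/N, S01=r/N, S11=(1-r²)/n + r²/N and D=S00+S11-2·S01. The weight on week 4 is w=(S00-S01)/D, and the variance on the week-4 scale is (S00·S11-S01²)/(D·w²).

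At n=N, w=.5 and the ratio follow-up : change : common baseline : two-wave is 1 : 2(1-r) : 1-r² : 2(1+r).

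**Worked case: r=.5, N=n=100.** Follow-up and change: .75/100 + .25/100 = .0100, so the pairwise SE is √(2×.0100)=.1414. Common baseline: .75/100 = .0075, SE √(2×.0075)=.1225. Noncentral t with 2n-2=198 df gives MDES .398 against .345, and power at d=.24 of 39% against 50%.

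**Pairwise, 100 per app, full retention (r=.3/.5/.7, unadjusted alpha)**

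| Contrast | MDES | Power at d=.24 |
|---|---|---|
| Follow-up | .398/.398/.398 | 39/39/39% |
| Change | .471/.398/.308 | 30/39/59% |
| Condition step without interaction | .642/.690/.734 | 18/16/15% |
| Common baseline | .380/.345/.284 | 43/50/66% |

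The MDES gain over the better of follow-up and change is 1-.380/.398=5%, 1-.345/.398=13% and 1-.284/.308=8%.

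**80% retention.** At r=.5, follow-up is .75/80 + .25/100 = .011875 and common baseline is .75/80 = .009375. Over the three r values, pairwise power goes from 33/34/51% (better of follow-up and change) to 35/41/56%, an MDES gain of 4/11/6%. The step without interaction carries 43/42/41% of the week-4 effect and has about 12-14% power.

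**Joint test**, one app differing from the other nine by d=.24: noncentral F with k-1 and k(n-1) df, λ=d²(1-1/k)/v. At r=.5 and full retention, λ=.0576×.9/.0100=5.18 for follow-up and change, and .0576×.9/.0075=6.91 for common baseline.

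| Design | Better of follow-up and change | Common baseline |
|---|---|---|
| 10 x 100, full retention | 29/29/49% | 32/39/57% |
| 10 x 100, 80% retention | 24/24/40% | 25/31/46% |
| 5 x 200, full retention | 67/67/90% | 72/81/94% |

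For 5 x 200, pairwise power goes from 67/67/87% to 71/79/92%.

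**Simulation** (10 x 100, complete data, 10,000 runs). Rejection under the null was .048-.055 for all four joint tests. Power at r=.5 for follow-up/change/two-wave/common baseline was .288/.281/.116/.384, in line with the formulas.

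**The case against.** The planned tests are valid under randomisation, so the loss is in precision alone. It is modest, and it depends on an r that the documents do not give. The 13% MDES gain at r=.5 is the peak, where the two planned contrasts tie; at r=.3 and 80% retention, power moves only from 33% to 35%. All of this stands and limits the size of the point. However, the common-baseline contrast is the most precise at every r shown, and the comparison is with the better planned contrast, which cannot be known in advance.

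The step without interaction may be only a rung in the model sequence, and the power paragraph's main effects belong to an ANOVA. That is fair: its low power matters only if the term is read as the app effect. One sentence in the plan would exclude that reading.

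A joint test may already be implied by comparing -2 log likelihood with and without the interaction. Whether that sentence reaches the main series is unclear. Even so, it would test change without a common baseline, and under REML such comparisons across different fixed effects need ML or a Wald/F test instead.

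The pairwise figures are unadjusted. With Bonferroni over all 45 pairs (10×9/2, an assumed rule), full retention and 100 per app, power is about 7/9/18% with the fix against 6/6/14%. The fix does not make pairwise claims well powered.

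**Conclusion.** The concern holds and should be acted on. It is about precision and a single named test, not about bias. Assuming equal variances and r of .3 to .7, the common-baseline contrast cuts variance by 9/25/15% at full retention relative to the better planned contrast. At 100 per app, this is worth about 3 to 10 percentage points of unadjusted pairwise or joint power for d=.24, and less at 80% retention. The conflict between 100 and 200 per condition remains. With ten apps, the joint test against d=.24 stays at 57% or below for r up to .7.

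**What to change.** For each of PHQ-9, GAD-7 and DERS-SF, pre-specify one REML model of baseline and week 4 with time and condition x time, **no condition main effect**, and an unstructured 2x2 covariance. The baseline mean is then common to all randomised conditions; with complete data this is in effect ANCOVA on baseline.

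- Name the joint F test of condition x time as the condition test for each outcome: 9 df for ten apps, or the number of conditions minus 1 if that number is revised.
- Take pairwise week-4 differences from the same model, under a stated multiplicity rule.
- State that the condition term from a step without interaction is not reported as an app effect.
- Drop the random time step, which the unstructured covariance replaces, or keep it without interpreting its variance.
- State in Procedures that the three scales are completed before randomisation.

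The cost is SAP wording only, provided the scales are in the first survey. If they are not, they must be added; otherwise neither the planned change models nor this model can be run. No person-level slope variance is estimated, which two waves could not support anyway. The intent-to-treat question is unchanged.

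### Each symptom scale gets two app comparisons, at follow-up and on change slope, with no rule for which one answers Question 3; at .05 each, the false-positive rate per scale is about 9-10%

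*Combined protocol and SAP*

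**What the plan says.** Question 3 under Aim 1 asks "Which apps result in reduced depression (PHQ-9), anxiety (GAD-7) and better emotional regulation (DERS"). It is a single question for each scale.

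The Analysis section answers it with mixed models for PHQ-9, GAD-7 and DERS-SF, which are "to test for condition differences at follow-up and change slope". The models start from a null model, "followed by models that add a random intercept, random time component, condition assignment, and condition x time interaction effects". Later in the section, after the dose-response models, it adds: "Model comparisons will apply -2 Log Likelihood, Akaike Information Criterion, and Bayesian Information deviance statistics".

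The only significance level in the documents is in the Sample Size and Power paragraph, where 1,000 participants "would be sufficient with a power of .80 and an alpha of .05" in an ANOVA F test. The documents name no primary outcome, no order of testing, no multiplicity adjustment, and no preference between the follow-up comparison and the slope comparison.

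**The concern.** Procedures describes randomisation to the apps and one assessment after baseline, at 4 weeks. With two time points, a difference in slope is a difference in mean change. Randomisation makes baseline means equal in expectation, so the difference in change and the difference at week 4 estimate the same quantity. They separate only through chance imbalance at baseline.

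The plan therefore has two tests of one effect and no statement of which one counts. An app whose users start slightly worse by chance can show a significant slope advantage and no significant week-4 difference, or the reverse. If either result can support a claim, each scale has two chances of a false positive. The findings are meant for rapid dissemination through suicide-prevention organisations, so a claim that an app works should rest on a contrast fixed in advance.

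**Working it through.** **Inputs from the documents.** Three symptom scales and two app comparisons per scale (Analysis). Ten apps with 100 per group, one assessment at 4 weeks, and expected retention of 80-100% (Procedures). Alpha .05, power .80, and "Cohen's d=.24 for main effect comparisons between any two conditions" with 200 per condition (Sample Size and Power).

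**Assumptions.** The documents give no correlation (rho) between baseline and week-4 scores, so I use .4, .6 and .8. I also assume equal SDs at the two times, full retention, and .05 for each comparison in the symptom models.

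**1. The plan's own figure.** For two groups of n and a two-sided test, the detectable difference is (1.960 + 0.842) × sqrt(2/n).
- n = 200: 2.802 × 0.100 = .280, not .24.
- n = 100: 2.802 × 0.1414 = .396.

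The stated .24 does not reproduce. That failure and the conflict between 100 and 200 per group are separate problems, and nothing below depends on them.

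**2. Correlation of the two comparisons.** In SD units the week-4 contrast has variance 2/n, the change contrast has variance (2/n) × 2(1 − rho), and their covariance is (2/n)(1 − rho). Their correlation is therefore sqrt((1 − rho)/2) = .55, .45 and .32 at rho = .4, .6 and .8.

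**3. False positives per scale, no true difference.**
- Ceiling if the two tests were independent: 1 − .95² = .0975, which is 1.95 times .05.
- One pair of apps, bivariate normal with the correlations above: .089, .092 and .095.
- Ten apps of 100, overall 9-df F test for each comparison, 20,000 simulated trials per setting: .092, .096 and .095. The simulation error is about sqrt(.095 × .905/20,000) = .002.
- Five conditions of 200 (rho .3 to .7): .088 to .092.
- Ten apps with 80 completers each (rho .3 to .7): .089 to .096.

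The result is about 9-10%, whichever group size is right and at either end of the expected retention, provided loss is unrelated to outcome. In the ten-app settings both comparisons are falsely significant together in only about 1% of trials or fewer, so a false positive on one usually comes with a null result on the other.

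**4. Disagreement when there is a true difference.** Take two apps with 100 each and a true week-4 d of .40, close to the .396 in step 1. Power is Phi(d/SE − 1.96). SE is sqrt(2/100) for follow-up, that value times sqrt(2(1 − rho)) for change, and that value times sqrt(1 − rho²) for week 4 adjusted for baseline.

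| rho | power, follow-up | power, slope | exactly one significant | power, week 4 adjusted for baseline |
|---|---|---|---|---|
| .4 | .81 | .73 | .24 | .87 |
| .6 | .81 | .89 | .20 | .94 |
| .8 | .81 | .99 | .19 | .997 |

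The two estimates differ in sign in only 0.2-0.7% of trials. Both being significant in opposite directions has a probability below one in a million.

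At the plan's own d of .24 with 200 per group, exactly one of the two is significant in about 30-31% of trials (rho .3 to .7).

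**The case against.** **The model-building sequence may supply the rule.** Condition enters before condition × time, and the first stated purpose is to test linear change. That gives some support for reading the slope as the natural answer to Question 3. If -2LL, AIC or BIC choose the model, two F tests at .05 are not exactly the planned procedure. These statistics compare model fit, however. No order of precedence is given, they can disagree, and none says which term decides between apps. Their placement after the dose-response models also leaves it unclear whether they cover the first series. The meaning of a condition difference at follow-up depends on how time is coded, which is not stated: with time zero at baseline, the condition term in the interaction model is a baseline difference. None of this names a deciding contrast.

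**The .05 is inferred.** This stands. The alpha belongs to the ANOVA power calculation, so the 9-10% is conditional on using it for the symptom models.

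**A reader might infer that the two comparisons can give opposite verdicts.** The arithmetic does not support that. The conflict is between one significant and one non-significant result, which correlated estimates of one effect produce by ordinary sampling. Part of it is a power gap: at rho = .8 the .19 is almost exactly 1 − .81, the rate at which the weaker test misses. Nor can the inflation exceed twofold, given the .0975 ceiling.

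**A reader might also infer that the analyst will report whichever test succeeds.** The documents do not suggest this. Both comparisons are specified in advance and neither is called confirmatory. What is missing is the rule.

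**This is one part of a wider multiplicity gap.** That also stands. The scales, the pairwise app contrasts and the dose-response models add further tests.

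**Conclusion.** The concern holds in limited form. The plan specifies two comparisons of the same randomised effect on each symptom scale and does not say which one answers Question 3. At an assumed .05 for each, the false-positive rate per scale is about 9-10% instead of 5%, for assumed correlations of .4 to .8. It cannot exceed .0975. At a true d of .40 with 100 per app, about 19-24% of trials would give a split result with no rule for reading it.

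This is a real ambiguity that should be settled before analysis. It does not invalidate the trial. Settling it leaves the multiplicity across scales: with an assumed correlation of .5 between scales, the chance of any false positive over the three is about 23-24% with both comparisons and still about 13-14% with one each.

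**What to change.** In the Analysis section, replace the two comparisons with one deciding contrast per symptom scale: the overall test of the week-4 difference between apps, adjusted for the same person's baseline score. It has 9 degrees of freedom with ten apps; the number follows the count of conditions once the 100 and 200 per group are reconciled.

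An overall test alone cannot say which apps work. If it is significant, follow it with pairwise app contrasts from the same model, adjusted for multiplicity. Report the unadjusted follow-up and slope contrasts descriptively, with intervals and no separate claim.

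The cost is a few sentences of plan text and the loss of the second test per scale. No new data are needed beyond the baseline scores that the slope model already requires; Procedures does not list the symptom scales at baseline, so it should say so. In the setting of step 4, the adjusted contrast has more power than either test it replaces. Multiplicity across the three scales needs its own rule.
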